6.4.4 Analysis of PFS and OS (Secondary)

PFS will be measured from the initial date of treatment to the date of documented progression, or the date of death (in the absence of progression), whichever occurs first. OS will be measured from the initial date of treatment to the recorded date of death.

PFS and OS will be estimated by the Kaplan-Meier method. The corresponding median survival times (with 95% confidence intervals) will be determined, as will the cumulative percentage of patients remaining progression-free (and the cumulative percentage-alive) at selected time points after initial treatment (e.g., 3, 6,12, 18 months). Log-rank test will be used to compare the PFS and OS between subgroups when event number permitted.

6.4.5 Correlative Translational Assays (Secondary)

Multiple lab outcomes will be compared between baseline and on treatment to examine the change in TME, metabolic profiling and cell hypoxia. These will also be compared between baseline and the value at the progression for progressors. All these pre vs post comparisons will be done with paired t-tests or Wilcoxon signed rank tests where appropriate. The change from pre- to post- treatment will be compared between subgroups (such as between responders and non-responders) with two sample t-test or Wilcoxon rank sum test where appropriate. The association of clinical response with tumor metabolism and with T cell function will be explored with logistic regressions. The association of survival endpoints (DOR, PFS, OS) with tumor metabolism and with T cell function will be explored with Cox proportional hazards models.

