4.0 METHODOLOGY

4.1.1 Subject Inclusion Criteria

In order to be eligible for participation in this trial, the subject must:

- 1. Be willing and able to provide written informed consent for the trial.
- 2. Be \geq 18 years of age on day of signing informed consent.

- 3. Have unresectable (stage III) or advanced (stage IV) cutaneous or mucosal melanoma. Patients with uveal melanoma are not eligible.
- 4. Progressed on prior anti-PD1 therapy with or without anti-CTLA4 therapy. Patients may have progressed in the adjuvant setting if treated within the last 6 months. Prior treatment with BRAF/MEK inhibitors permitted, however, not required. Progression must be radiographic, and progression of disease will be confirmed by a radiologist. Patients must have progressed during anti-PD-1 therapy, defined as unequivocal progression on or within 3 months of the last dose of anti-PD-1 therapy if treated in the metastatic setting, or within 6 months if treated in the adjuvant setting.
- 5. Have measurable disease based on RECIST 1.1.
- 6. Patients do not have to have biopsiable disease to be eligible. However, patients with biopsiable disease must undergo biopsy at study entry and at week 12.
- 7. Have a performance status of 0 or 1 on the ECOG Performance Scale.
- 8. Demonstrate adequate organ function as defined in Table 1. All screening labs should be performed within 14 days of treatment initiation.

Table 1: Adequate Organ Function Laboratory Values

Criston	Laboratory Volus			
System	Laboratory Value			
Hematological				
Absolute neutrophil count (ANC)	≥1,000 /mcL			
Platelets	≥50,000 / mcL			
TT 11.	≥7 g/dL without transfusion or EPO dependency (within 7 days			
Hemoglobin	of assessment)			
Renal				
Serum creatinine OR	≤1.5 X upper limit of normal (ULN) OR			
Measured or calculated creatinine	\ \ \ \ \ \ \ \ \ \ \ \ \ \ \ \ \ \ \			
clearance	\geq 60 mL/min for subject with creatinine levels \geq 1.5 X			
(GFR can also be used in place of	institutional ULN			
creatinine or CrCl*)				
Hepatic				
Serum total bilirubin	≤ 1.5 X ULN OR			
	Direct bilirubin ≤ ULN for subjects with total bilirubin levels >			

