6.3 Sample Size and Accrual

The null hypothesis that the true ORR is 10% will be tested versus a one-sided alternative of 25% or higher, using Simon's minimax two-stage design. In the first stage, 16 patients will be accrued. If there are <2 responses, the study will be stopped and alternative doses of axitinib considered. If at least 2 responses are observed, 15 additional patients will be enrolled in the 2nd stage. The combination therapy will be regarded as worthy of further study if ≥6 responses are observed in both stages. Total sample size is 31 patients. This design has a type I error rate of 0.08 with a power of 0.81 when the true response rate is 0.25. Secondary endpoints of this study are PFS, OS and safety. Survival endpoints (PFS and OS) will be estimated with the Kaplan-Meier method, and compared between marker value groups with the log-rank test. We will also perform extensive correlative analysis (flow, IHC, metabolic analyses).

The accrual rate of the trial is estimated to be 1-2 patients/month, therefore, we will be able to finish the accrual of the study in approximately 24 months.

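### With few responders expected, a penalised fit would make the marker-response models in 6.4.5 more accurate, and duration of response by marker is better described than modelled

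*Combined protocol and SAP*

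**What the plan says.** Section 6.4.5 (Correlative Translational Assays) plans two kinds of regression on the laboratory markers. For response: "The association of clinical response with tumor metabolism and with T cell function will be explored with logistic regressions". For time-to-event outcomes it addresses "The association of survival endpoints (DOR, PFS, OS) with tumor metabolism and with T cell function", using Cox proportional hazards models. The section gives no penalised or exact method, no limit on the number of markers per model, and no rule for separation or for very few responders. Section 6.4.4 has a condition on the number of events, but it covers only the log-rank comparison of PFS and OS.

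The numbers come from Section 6.3: "Total sample size is 31 patients", and "The null hypothesis that the true ORR is 10% will be tested versus a one-sided alternative of 25% or higher". The first stage has 16 patients, and "If there are <2 responses, the study will be stopped". Section 4.1.1 (item 6) adds "Patients do not have to have biopsiable disease to be eligible", although patients who can be biopsied must be.

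Two other places bear on this point. Section 6.4.2 includes stable disease in the definition of ORR. Section 2.4 lists the correlative work under exploratory objectives, while the heading of 6.4.5 calls it secondary.

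**The concern.** Ordinary maximum likelihood for a logistic model is biased away from zero when the rarer outcome is scarce. It has no finite solution when a marker separates responders from non-responders completely. Duration of response exists only in responders, so a Cox model for it rests on a handful of events.

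The link between marker and response is the mechanistic question of the trial: Section 2.3 attributes the hoped-for gain in response to less hypoxia and less T cell dysfunction. An odds ratio that comes out too large, or a hazard ratio driven by three or four patients, would be a poor basis for planning a follow-on study.

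**Working it through.** **1. The plan's own figures.** Inputs from Section 6.3: 16 patients in stage 1, stop with 0 or 1 response, 31 in total, success with at least 6 responses, p0 = 0.10, p1 = 0.25. The probability of success is the sum over k = 2 to 16 of P(X1 = k) × P(X2 ≥ 6 − k), with X1 ~ Bin(16, p) and X2 ~ Bin(15, p). This gives 0.0788 at p = 0.10 and 0.805 at p = 0.25, which match the stated 0.08 and 0.81.

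**2. How many responders (CR or PR).**

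- Simple expectation: 31 × 0.25 = 7.75 and 31 × 0.10 = 3.1.
- Stage 1 stop at 10%: 0.9^16 + 16 × 0.1 × 0.9^15 = 0.185 + 0.329 = 0.51. Those trials end with 0 or 1 responder among 16, and no regression is useful.
- Expected responders at 10% if the trial continues: (1.6 − 0.329)/(1 − 0.515) + 15 × 0.1 = 2.62 + 1.5 = 4.1.
- The same at 25%, where P(X1 = 0) = 0.010 and P(X1 = 1) = 0.053: (4 − 0.053)/(1 − 0.063) + 3.75 = 4.21 + 3.75 = 7.96.
- Biopsied subset: its size is not stated. If it were 20 (an assumption), 20 × 0.10 = 2 to 20 × 0.25 = 5 responders would be expected before allowing for stage 1.

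**3. Ordinary versus Firth logistic regression, by simulation.** There is one standard normal marker. The marker effects are assumptions, because the documents give none. Ordinary-fit results leave out separated data sets.

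At n = 31, ORR 25% and true log odds ratio 1.10 (odds ratio 3), over repeated simulation runs:

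| | Ordinary | Firth |
|---|---|---|
| Mean log odds ratio | 1.32 to 1.37 | 1.10 to 1.15 |
| Median log odds ratio | 1.15 to 1.19 | 0.99 to 1.03 |
| Root mean squared error | 0.88 to 0.93 | 0.71 to 0.73 |
| Median absolute error | 0.42 | 0.36 to 0.37 |

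At n = 31 with the number of responders fixed at 3, 5 and 8:

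| True odds ratio | Ordinary, geometric mean | Firth, geometric mean |
|---|---|---|
| 1 | 1.00 / 1.01 / 0.99 | 0.99 / 1.01 / 0.99 |
| 2 | 2.52 / 2.48 / 2.29 | 1.99 / 2.09 / 2.04 |
| 4 | 7.15 / 5.97 / 5.44 | 4.04 / 4.06 / 4.00 |

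The ordinary mean is therefore 15 to 26% too high at a true odds ratio of 2, 36 to 79% too high at 4, and unbiased at 1. Root mean squared error at odds ratio 2 is 1.35 / 0.88 / 0.59 for the ordinary fit and 0.70 / 0.60 / 0.47 for Firth. Coverage of the 95% profile penalised-likelihood interval is 0.955 to 0.973.

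**4. Separation.** With one marker and n = 31 it occurs in 0 to 0.4% of data sets at odds ratio 2 and in 0.2 to 5% at odds ratio 4. With three covariates, 3 responders and odds ratio 4, it reaches 19% at n = 31 and 30% at n = 20. With one marker at n = 20, ORR 10% and odds ratio 3, it is about 12%.

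**5. Cox model for DOR.** Assumed hazard ratios are 1, 2 and 4, with 0 or 40% censoring. The share of trials without a finite estimate is 34 to 62% with 3 responders, 3 to 33% with 5, and 0 to 10% with 8. A Firth Cox fit does not rescue 3 responders: its root mean squared error is about 1.7 to 2.8 on the log scale, no clear gain over the ordinary fit. Even a finite estimate is imprecise. With 4 events (assumed), the standard error per SD of the marker is about 1/√4 = 0.5, so the 95% limits are the estimate multiplied by exp(±1.96 × 0.5), that is by about 0.4 and 2.7.

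**6. What the Firth fit gives up.** At a true odds ratio of 4 its median estimate is about 3.4 to 3.6. The mean predicted response probability rises from 0.097 to 0.12 with 3 of 31 responders, and from 0.258 to 0.27 with 8 of 31. With 3 responders and odds ratio 4 it rejects in 0.57 of trials, against 0.65 for the ordinary likelihood-ratio test and 0.19 for the Wald test.

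**The case against.** The strongest reply is that this matters little. The models are described as explored and drive no decision. Section 6.4.2 already has Fisher's exact tests between marker groups, and 6.4.5 has rank-sum comparisons of responders with non-responders. The plan does not name the estimator, so a Firth fit would comply as the text stands. The typical bias is small, since the median ordinary estimate is 1.15 to 1.19 against a true 1.10, and the large gaps in root mean squared error come from a few extreme fits whose wide intervals would give them away.

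Most of this stands, and it is why the point is minor. It does not remove the point. Logistic regression without qualification will be run as ordinary maximum likelihood, and Firth also had the smaller median absolute error (0.36 to 0.37 against 0.42).

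A reader might infer four stronger things that the documents and figures do not support:

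- **A null marker will look predictive.** It will not: the ordinary fit is unbiased at odds ratio 1.
- **The logistic models will generally fail to converge.** With one marker at n = 31 that is uncommon. It becomes a real risk with several covariates, which the plan does not rule out, or in a small biopsied subset.
- **A trial that reaches 31 patients at ORR 10% will typically have about 3 responders.** The stage 1 rule makes that about 4, and about half of such trials never reach 31.
- **The penalised fit is free.** It needs no patients or procedures, but it has the small losses in step 6.

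It can also be said that dropping the DOR Cox model replaces an imprecise estimate with none. At 3 to 5 responders there is often no estimate to lose, and a listing shows the same data without implying precision.

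**Conclusion.** The point holds as a cheap improvement of low severity. When a real association exists, ordinary logistic regression at this size overstates the log odds ratio on average (about 1.3 for a true 1.10 at n = 31 and ORR 25%) and has larger error than a Firth fit (about 0.9 against 0.7). The typical overstatement is much smaller. The DOR Cox model is the weaker of the two analyses, because with 3 to 5 responders it often has no finite estimate.

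The result rests on assumed marker effects, a single normally distributed marker, and assumed DOR censoring. Any figure for n = 20 rests on an assumed biopsied subset. The responder counts assume CR plus PR. If stable disease counts, as Section 6.4.2 has it, there would be more responders, but the bias remains: with an assumed 15 of 31, the ordinary fit gives 2.26 for a true odds ratio of 2 and 5.22 for 4. The primary test is not affected.

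**What to change.** First reconcile the response definition in Section 6.4.2 with the 10% and 25% rates in Section 6.3, so that it is clear who counts as a responder. Then, in Section 6.4.5:

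- Specify Firth-penalised logistic regression with profile penalised-likelihood intervals, one marker per model.
- Replace the Cox model for DOR with a listing or Kaplan-Meier display of DOR by marker value. Keep Cox models for PFS and OS.
- State that marker results will be descriptive only if the trial stops at stage 1 with 0 or 1 responder.

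The cost is a few lines of SAP text and standard software, with no extra patients or procedures. The statistical price is slight shrinkage of the median estimate, slightly raised predicted response probabilities, and somewhat fewer rejections than the ordinary likelihood-ratio test.

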2.3 Primary Objective(s) & Hypothesis(es)

(1) Objective: To assess the overall response rate (ORR) of nivolumab plus axitinib in patients with anti-PD1 refractory melanoma as measured by clinical tumor measurement and radiologic tumor measurement by CT scans at baseline and after 12 weeks of treatment.

Hypothesis: Patients treated with nivolumab and axitinib will have a response rate greater than the estimated response rate in anti-PD1 refractory patients, which is approximately 10%. We propose this improved response will be due to a reduction of intra-tumoral hypoxia and resultant T cell dysfunction.

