5.1.2.5 Tumor Imaging and Assessment of Disease

PET/CT and CT

- -At baseline and week 12, extra-cranial tumor assessment will be conducted with contrast-enhanced PET/CT or CT and applied using RECIST 1.1 criteria.
- -A screening scan will be performed prior to enrollment unless a recent (within 28 days of enrollment) scan is available. Target and non-target lesions must be identified at time of screening scan and the same lesions must be re-assessed at each restaging scan.
- -Repeat PET/CT or CT imaging will be obtained at week 12, and then CT will be obtained at 12 week intervals.
- -Complete response/partial response confirmation assessments must take place at least 4 and up to 12 weeks after the documentation of initial response. If the last radiographic assessment for extra-cranial disease was more than 8 weeks prior to discontinuation from study and progressive disease has not been documented, disease assessment should be obtained at the time of study discontinuation.
- -If patients have PD by RECIST 1.1 criteria, the Immune Related Response Criteria (irRC) will be used for assessment of tumor response for the purposes of managing patients on protocol treatment and decision making for discontinuation of study therapy due to disease progression. These disease assessments will be performed by the investigator with site radiology reading.
- For the purposes of the secondary efficacy endpoint of the study, response assessment based on RECIST 1.1 will be applied as the primary measure and irRC by investigators will be evaluated as a secondary assessment only if patient have PD by RECIST 1.1. If patients have PD by RECIST 1.1 but have SD or PR by irRC, they will be permitted to continue treatment. In order for a patient to continue to receive study treatment beyond progression by RECIST 1.1, in addition to having SD or PR by irRC, patients must not have symptoms or signs of disease progression, including significantly worse laboratory values or a decline in ECOG performance status.
- At the time of radiographic progression of disease, if treatment is to continue beyond PD, patients will be re-consented and adequately informed of all FDA-approved therapy, and potential clinical benefit, that the patient may be foregoing in order to continue receiving the investigational product.

MRI

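### Section 6.4.5 relates baseline markers to response only as responder yes/no and leaves the scheduled week-12 lesion measurements unused

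*Combined protocol and SAP*

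**What the plan says.** Section 6.4.5 contains two analyses that involve tumour response.

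- Association with markers: "The association of clinical response with tumor metabolism and with T cell function will be explored with logistic regressions".
- Change in markers from before to after treatment: "compared between subgroups (such as between responders and non-responders) with two sample t-test or Wilcoxon rank sum test where appropriate".

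Neither uses the amount of tumour shrinkage or growth. The same section also plans paired pre/post tests of the markers and Cox models for DOR, PFS and OS. None of those uses a responder split as its outcome.

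The continuous measurement is already scheduled. Section 4.1.1 requires RECIST-measurable disease, the flow chart in Section 5.1 puts the first on-treatment scans at week 12, and Section 5.1.2.5 says: "Target and non-target lesions must be identified at time of screening scan and the same lesions must be re-assessed at each restaging scan".

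Two other passages matter. Section 6.4.1 foresees patients who progress clinically and never return for a scan. Section 6.4.2 counts SD, along with CR and PR, in the response rate.

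**The concern.** RECIST response is largely a cut of a continuous quantity, the change in the sum of target-lesion diameters. The cut is the right basis for the Simon go/no-go decision. It is a weak outcome for studying markers in a trial this small: at the plan's own response rates it leaves about 3 to 8 responders among 31 patients. There may be fewer with tumour markers, because Section 4.1.1 does not require biopsiable disease. In the response analyses, a patient with 25% shrinkage and one with 60% growth count the same.

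What is at stake is the link between markers and response. Section 2.3 states: "We propose this improved response will be due to a reduction of intra-tumoral hypoxia and resultant T cell dysfunction". If a real, moderate association between a baseline marker and shrinkage is missed because the outcome was cut in two, the trial could wrongly suggest that the marker carries no information about response.

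**Working it through.** **1. The plan's own figure.** Section 6.3 states the hypotheses: "The null hypothesis that the true ORR is 10% will be tested versus a one-sided alternative of 25% or higher". Stage 1 takes 16 patients and needs two responses to go on; stage 2 then adds 15. The final criterion is: "The combination therapy will be regarded as worthy of further study if ≥6 responses are observed in both stages". The probability of a positive result is

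Σ (k = 2 to 16) P[Bin(16, p) = k] × P[Bin(15, p) ≥ 6 − k].

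This gives 0.0788 at p = 0.10 and 0.8053 at p = 0.25, against the stated 0.08 and 0.81. The design inputs are sound. These are the only power figures in Section 6; none is given for the correlative analyses.

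**2. Responders available.** 31 × 0.10 = 3.1 and 31 × 0.25 = 7.75. With 20 patients who have tissue (assumed), 20 × 0.25 = 5.

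**3. Information kept by the cut.** For a weak association under normality, the efficiency of a split with fraction q is φ(z)² / [q(1 − q)], where z is the normal quantile at 1 − q. At q = 0.25, 0.318² / 0.1875 = 0.54. At q = 0.50, which is an assumption for a split that counts SD, 0.399² / 0.25 = 0.64.

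**4. Baseline markers: simulated power, two-sided 0.05.** Marker and latent tumour change are bivariate normal with correlation ρ, and responders are the best 25%. A share of the worst patients is tied at the worst rank. N = 31 and the 25% come from Section 6.3; everything else is assumed. The table shows Spearman against the t-test when response follows week-12 change exactly. Gains in points are taken before rounding.

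| n | ρ | 20% tied | Gain | 35% tied | Gain |
|---|---|---|---|---|---|
| 20 | 0.3 | 0.22 vs 0.15 | 7 | 0.22 vs 0.15 | 7 |
| 20 | 0.4 | 0.38 vs 0.24 | 14 | 0.36 vs 0.24 | 12 |
| 20 | 0.5 | 0.57 vs 0.36 | 21 | 0.53 vs 0.36 | 18 |
| 25 | 0.3 | 0.29 vs 0.19 | 11 | 0.26 vs 0.18 | 8 |
| 25 | 0.4 | 0.46 vs 0.30 | 16 | 0.43 vs 0.30 | 14 |
| 25 | 0.5 | 0.68 vs 0.46 | 23 | 0.65 vs 0.45 | 20 |
| 31 | 0.3 | 0.33 vs 0.22 | 12 | 0.32 vs 0.22 | 10 |
| 31 | 0.4 | 0.56 vs 0.37 | 19 | 0.53 vs 0.36 | 16 |
| 31 | 0.5 | 0.78 vs 0.55 | 23 | 0.75 vs 0.55 | 21 |

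Logistic regression, adjusted to its nominal size, is within two points of the t-test throughout. The rank sum test does slightly worse than the t-test: with 30% tied, n = 31 and ρ = 0.5, Spearman has 0.77, the t-test 0.55 and the rank sum test 0.52. Over the three tie shares and both two-group tests, the gain is about 7 to 26 points. Spearman's null rejection rate stays at 0.046 to 0.058.

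**5. Imperfect link.** Let measured week-12 change be λ × latent change + √(1 − λ²) × noise, with response still set by the latent change. At n = 31, ρ = 0.5 and 30% tied:

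- λ = 0.8: Spearman 0.65 against 0.53 to 0.57.
- λ = 0.6: Spearman 0.57 against 0.52 to 0.55.

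Over n = 20 to 31 and ρ = 0.3 to 0.5, the gain is about 2 to 12 points at λ = 0.8 and about 0 to 6 at λ = 0.6.

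**6. Marker changes.** These need week-12 tissue. If the worst 30% have none and drop out (assumed), about 0.7 × 31 ≈ 22 patients remain. At ρ = 0.5:

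| n enrolled | λ | Spearman | Rank sum | t-test |
|---|---|---|---|---|
| 31 | 1.0 | 0.36 | 0.26 | 0.30 |
| 31 | 0.8 | 0.19 | 0.26 | 0.29 |
| 31 | 0.6 | 0.10 | 0.25 | 0.28 |
| 20 | 1.0 | 0.24 | 0.16 | 0.20 |
| 20 | 0.8 | 0.13 | 0.15 | 0.18 |

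Here the continuous analysis wins only when the link is close to exact.

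**The case against.** The strongest objection is that response in this protocol is not simply a cut of week-12 diameter change. Scans repeat every 12 weeks, CR and PR need confirmation 4 to 12 weeks later, and RECIST also uses non-target and new lesions. A link below 1 is therefore realistic and the gain shrinks accordingly. This stands, and it is why the size is given by link.

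A second objection is that the work is exploratory. Section 2.4 lists it so, Section 6.4.5 says explored and names responders only as an example, and Section 9.3 mentions exploratory volumetric assessment. Nothing forbids a continuous analysis. That limits the seriousness of the point, but an analysis added after the data are seen is worth less than one specified now.

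Four stronger readings are tempting, and the documents do not support them:

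- That every patient will have a week-12 measurement. Re-measurement is scheduled for all, but Section 6.4.1 expects some clinical progressors without a scan.
- That the whole mechanistic hypothesis loses power. The paired tests ask directly whether hypoxia and T cell function change, and the Cox models of PFS and OS still separate early from late progressors among non-responders.
- That one figure for lost power follows from the plan. It depends on inputs that the documents do not give; at a correlation of 0.2 the loss is only about 0 to 8 points even with no ties and an exact link.
- That percent change should replace the responder comparison everywhere. For marker changes, step 6 shows that this can reduce power.

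**Conclusion.** The point holds for baseline markers. Relating them to response only as yes/no discards usable information. Under correlations of 0.3 to 0.5, 25% responders, 20 to 31 patients and early progressors tied at the worst rank, the cost is about 7 to 26 points of power with an exact link, about 2 to 12 at a link of 0.8, and about 0 to 6 at 0.6. The correlation, the link, the share of early progressors and the number of patients with tissue are all assumptions.

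The point does not extend to marker changes, where the planned comparison may be the better one. Nor does it promise adequate power: at n = 31 and a correlation of 0.3, the Spearman analysis reaches only 0.32 to 0.33 even with an exact link. The primary ORR analysis and the Simon rule are not affected.

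**What to change.** Amend Section 6.4.5 as follows.

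1. **Baseline markers.** Add a pre-specified Spearman rank correlation, with confidence interval, between each baseline marker and the percent change to week 12 in the RECIST 1.1 sum of target-lesion diameters. Give the worst rank to patients with new-lesion progression, clinical progression or death by week 12. Report it beside the logistic model.
2. **Marker changes from baseline to week 12.** Keep the responder versus non-responder comparison. Show percent change only as a supplementary description, and state how many patients lack week-12 tissue.
3. **Definition.** State that responder in this section means CR or PR, because Section 6.4.2 also counts SD.
4. **No change** to the primary ORR, the Simon rule, the paired tests or the Cox models.

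The cost is SAP wording; no scans, biopsies or patients are added. The downside is that percent change ignores non-target lesions and responses that come after week 12, and that it depends on the worst-rank convention. This is why the logistic model stays beside it.
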